COMIRB Protocol

COLORADO MULTIPLE INSTITUTIONAL REVIEW BOARD
[name] [contact] [contact]

Protocol #: 16-1965

Project Title: Management of diabetic ketoacidosis in children: does early glargine prevent rebound hyperglycemia?

Short Title: "Early glargine in DKA"

Principal Investigator: [name]

Co-investigators: [name] [name]; [name], PhD

Version Date: 11/6/2017

I. Hypotheses and Specific Aims:

Hypothesis 1 (Primary outcome): Early administration of glargine in the treatment of DKA in children will result in reduced rebound hyperglycemia compared to those given standard-of-care management.

Specific Aim 1 (Primary outcome): To evaluate the rate of rebound hyperglycemia (serum glucose level of greater than 180 mg/dL (>10 mmol/L) within 12 hours after discontinuation of IV insulin) in children treated for diabetic ketoacidosis (DKA) with early glargine versus standard-of-care management.

Hypothesis 2: Early administration of glargine in the treatment of DKA in children will result in a reduced rate of recurrent ketogenesis compared to those given standard-of-care management.

Specific Aim 2: To evaluate the rate of recurrent ketogenesis (beta-hydroxybutyrate ≥ 1.5 mmol/L within 12 hours after discontinuation of IV insulin) in children treated for diabetic ketoacidosis (DKA) with early glargine versus standard-of-care management.

Hypothesis 3: The risk of hypoglycemia will not differ between those given early administration of glargine versus those given standard-of-care management:

- a. Early administration of glargine in the treatment of DKA in children will not increase hypoglycemic events compared to those given standard-of-care management.
- b. Rate of blood glucose decrease while on IV insulin in children with DKA will not be different between those given early administration of glargine versus those given standard-of-care management.
- c. Participants who received early glargine will not need more frequent reductions in the IV insulin rate than those given standard-of-care management.

Specific Aim 3: To determine the risk of hypoglycemia between those given early administration of glargine versus those given standard-of-care management.

- a. Assess the frequency of hypoglycemic events during treatment of DKA, and within 12 hours after discontinuation of IV insulin, in children given early glargine versus standard-of-care management.

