 - Percent of patients with blood glucose > 180 mg/dL.
 - Median blood glucose.
 - Percent of time with blood glucose > 180 mg/dL.
2. Rate of recurrent ketogenesis (serum beta-hydroxybutyrate \geq 1.5 mmol/L) within 12 hours (or until time to hospital discharge if less than 12 hours) after discontinuation of IV insulin.
 - Rate of late-recurrent ketogenesis (serum beta-hydroxybutyrate \geq 1.5 mmol/L) 12-18 hours after discontinuation of IV insulin for participants who remain hospitalized for over 24 hours.
3. Frequency of hypoglycemic events while on IV insulin (and within 12 hours after discontinuation of IV insulin) on glucometer or CGM.
 - Glucometer: percent of patients with blood glucose < 70 mg/dL (+/- 2 hours of an "index" hypoglycemic event).
 - CGM: % of time with blood glucose < 70 mg/dL.
4. Rate of blood glucose decrease while on IV insulin on glucometer and CGM within the following time points: 0-2 hours, 2-4 hours, 4-6 hours, >6 hours.
5. Number of participants who needed a decrease in their IV insulin rate (secondary to hypoglycemia).
6. Feasibility of using CGM as a tool for glucose monitoring in DKA.
 - Percent of CGM failures during treatment of DKA.
 - Correlation of CGM to POC glucose monitoring during DKA.

B. Description of Population to be Enrolled:

Eligible patients will be enrolled from Children's Hospital Colorado Emergency Department; a large tertiary care ED and level I trauma center in Aurora, Colorado. These will be patients with either a known diagnosis of T1D presenting in DKA or a new diagnosis of T1D presenting in DKA (see inclusion criteria). Patients will be enrolled either by the PI or a member of the study team (who will be available between the hours of 8:00 am and midnight). Depending on study team member availability, and due to the variability of time of presentation to the ED, patients who present outside of these hours may not be able to be enrolled into the study.

In this study we aim to approach 100 participants, both males and females aged 6-17.99 years, who present in DKA. Assuming 80% of participants approached will be eligible to participate and 60% of eligible subjects will consent to participate, this provides at least 48 subjects, which is needed for 80% power to detect an absolute difference of 40% difference in the rate of rebound hyperglycemia.

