Data from adult studies cannot be directly translated into the care of children in DKA given the increased risk of cerebral edema in children and more concern regarding hypoglycemia (both in the hospital and in an ambulatory setting). Therefore, a study looking at the benefits

and safety of giving glargine early in DKA needs to be completed in children and adolescents. We see a large number of patients across the age range of 6 to 18 years who present in DKA and, therefore, expect to obtain a full age distribution in our study participants. Additionally, it is highly possible that younger children respond to DKA management differently than older children and adolescents, therefore, potential sub-analyses within different age groups may need to be utilized.

Inclusion Criteria:

Children meeting the following criteria will be considered for enrollment:

1. Age 6-17.9 years at time of enrollment.
2. Known history of T1D defined as: ≥ 1 positive autoantibody (IAA, GAD, IA-2, or ZnT8), HbA1c $\geq 6.5\%$, and insulin requirement. Those with a presumed diagnosis of T1D (new onset diagnosis) based on age and presentation will be included in the study and their autoantibody status and HbA1c status will be determined once these results are available. Only those with a diagnosis of T1D (defined above) will be included in the data analysis.
3. Diagnosis of DKA (serum glucose or fingerstick glucose concentration ≥ 200 mg/dL, venous pH ≤ 7.3 and/or serum bicarbonate concentration ≤ 15 mmol/L, and presumed ketonemia or ketonuria). Confirmation of ketonemia or ketonuria will be made once these results are available.

Exclusion Criteria:

The following participants will be excluded from the study:

1. Participants who present in DKA with known conditions that affect neurological function such as: suspected alcohol or drug use, severe head trauma, meningitis, etc., that would compromise routine neurological assessment during DKA treatment.
2. Other known complicating illness or poorly-controlled chronic illness that is known to affect blood glucose levels and/or electrolyte balance such as: chronic renal disease (requiring hemodialysis), chronic liver disease (with evidence of current hepatic dysfunction, coagulopathy, and/or chronic hepatitis), or severe chronic lung disease (requiring the use of oral glucocorticoids).

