- Upon diagnosis of DKA patients will begin rehydration with standard fluid therapy using an initial IV bolus of 10mL/kg of 0.9% saline.
- Fluid boluses may be repeated at the discretion of the treating physician to restore hemodynamic instability.
- During initial therapy, study personnel will obtain informed consent. .
- Participant Data: basic information such as name, date of birth, race/ethnicity, and diagnosis will be collected.
- Randomization:
 - We will use a blocked, stratified randomization scheme to allocate participants 1:1 to treatment groups. Randomization will be stratified within new onset and existing T1D patients to ensure balance across treatment groups.
 - Ideally, randomization will occur during the initial fluid bolus, however, if this is not possible then the patient will be treated with the standard DKA protocol for this study site until consent is completed, but not beyond the time frame outlined in the exclusion criteria.
 - Participants will be randomized into one of two groups:
 - 1. Early glargine, study group (N ~ 25):**
 - a. Administer glargine SQ x 1 when pH \geq 7.10.
 - b. Primary investigator and/or on-call co-investigator to determine glargine dose:
 - i. New onset T1D: 0.3 units/kg
 - ii. Established T1D: use home total daily dose (TDD) of long-acting insulin (or TDD of basal if on an insulin pump), converted to glargine equivalents.
 - 2. Standard-of-care, control group (N ~ 25):**
 - a. Administer glargine SQ x 1 at time of correction of acidosis (venous pH \geq 7.3 and serum bicarbonate \geq 18 or BHB \leq 1) and discontinuation of IV insulin.
 - b. Primary investigator and/or on-call co-investigator to determine glargine dose as described above.
- After initial fluid bolus(es), standard insulin therapy begins with a continuous infusion of IV regular insulin at a rate of 0.1 units/kg/hr.
- Ongoing rehydration is established using IV fluids with $\frac{3}{4}$ normal saline at a standard rate of 1.5 x maintenance unless this is determined to be harmful by the primary attending physician.
- Potassium replacement is provided using IV fluids containing potassium acetate and potassium phosphate.
- When serum glucose concentration declines below 250 mg/dL, dextrose (5-12.5%) is added to the IV fluids to maintain serum glucose between 100 mg/dL and 200 mg/dL.

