- If more than 12.5% dextrose IV fluids are needed to maintain serum glucose between 100 mg/dL and 200 mg/dL, the IV insulin rate will be decreased by 0.01 units/kg/hr.

Laboratory Monitoring during DKA treatment:

- Blood glucose concentration is obtained at presentation and hourly while on IV insulin using a point-of-care glucometer or serum measurements.
- Venous pH, serum electrolytes (Na, K, Cl, HCO₃, BUN, creatinine) are obtained at presentation and then every 2-4 hours while on IV insulin.
- Serum beta-hydroxybutyrate (BHB) will be obtained at presentation and then every 6 hours while on IV insulin until \leq 1.0 mmol/L.
- HbA1c will be obtained at presentation.

Continuous Glucose Monitoring (CGM): An option to have CGM sensor placed will be discussed with participant and/or primary guardian. The CGM system used during this study will be the Abbott FreeStyle Libre Pro Flash® Glucose Monitoring System (Figure 2).

Figure 2: Abbott FreeStyle Libre Pro Flash® Glucose Monitoring System:

<http://www.freestylelibrepro.us/blood-glucose-monitoring-device.html>

The FreeStyle Libre Pro® uses a small low-profile sensor approved for up to 14 days of wear in the USA by the FDA and has shown an average mean absolute relative difference (MARD) of 11.4% over 14 days of continuous wear. The Libre is also marketed as being free from interference with acetaminophen, eliminating this as a concern in our population as this is a common medication used in pediatrics. Further, this system does not require calibration and is blinded from the participant. Data will be available to study personnel at time of download after 1 week of wear.

CGM protocol:

- Following informed consent, an area on the back of the upper arm will be cleaned with an isopropyl alcohol solution and the CGM sensor system will be placed by trained study personnel.
- The CGM sensor placement will ideally occur after initial rehydration has been established, however, if this is not possible the CGM can be placed on the participant at any time during the initial 12 hours of DKA management.
- The CGM sensor will remain on the participant for the duration of hospitalization and an additional week following discharge.
- If a CGM sensor malfunctions during the participant's hospitalization, a new sensor can be replaced by study personnel as soon as possible following knowledge of the malfunction.

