The data collected by CGM will be summarized for each patient and day into variables describing glycemia, such as mean glucose, area under the curve, area under the curve >180 mg/dL, and percent of time spent above or below particular glucose thresholds (e.g., >180, <60, and <70 mg/dL). Trends over time in these summary statistics will be evaluated graphically to give insight into blood glucose response during treatment of DKA and immediately after resolution of DKA. For variables without an excess of zero values, we will use linear mixed-effects models to compare trajectories over time in the two groups. We will also calculate the mean value of each of these statistics for each patient and compare the groups using t-tests or nonparametric equivalent. Bland-Altman plots will be used to evaluate the agreement between CGM glucose variables (e.g., mean glucose) and POC glucose. To interpret the clinical relevance of any discrepancies between the two sets of measures, we will use Clarke error grid analysis, which classifies pairs of blood glucose measurements made by two methods into categories based on the impact the discrepancy would have on treatment decisions.

VIII. Summarize knowledge to be gained:

Limited data suggest that administration of glargine early in DKA management may reduce rebound hyperglycemia, recurrent ketogenesis, and overall hospital length of stay; however, this has not been well-studied in children. Given the increasing incidence of T1D in youth, frequency of DKA, and hospitalizations secondary to DKA, a smoother transition to subcutaneous insulin could reduce in-hospital morbidity and overall cost per admission. Therefore, we propose to evaluate the effects of early glargine in pediatric DKA management. Additionally, there currently are no known studies using CGM technology in DKA in children evaluating rebound hyperglycemia and the transition to subcutaneous insulin. Therefore, these data will be vital in assessing our primary and secondary outcomes and in broadening our understanding of DKA management in this population.

IX. References:

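### No analysis is named for the rate of glucose fall (Hypothesis 3b), and no method in the plan uses the presentation glucose already recorded, so an unadjusted comparison would lose precision

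*Combined protocol and SAP*

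**What the plan says.** Hypothesis 3b (Section I) states: "Rate of blood glucose decrease while on IV insulin in children with DKA will not be different" between the arms. It gives no margin. The matching outcome, number 4 under Secondary outcomes in Section IV.A, is "Rate of blood glucose decrease while on IV insulin on glucometer and CGM within the following time points: 0-2 hours, 2-4 hours, 4-6 hours, >6". The zero point of these windows is not defined.

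The starting level is collected. Section IV.C.2.1, Laboratory Monitoring, says: "Blood glucose concentration is obtained at presentation and hourly while on IV insulin using a point-of-care glucometer or serum measurements". Two protocol rules bear on how far glucose can fall:

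- **Entry.** Inclusion criterion 3 requires "serum glucose or fingerstick glucose concentration ≥ 200 mg/dL", with no upper limit.
- **Dextrose.** Section IV.C.2.1 says: "When serum glucose concentration declines below 250 mg/dL, dextrose (5-12.5%) is added to the IV fluids", with a target of 100 to 200 mg/dL.

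On allocation, the same section says: "Randomization will be stratified within new onset and existing T1D patients to ensure balance across treatment groups". Glucose is not a stratification factor.

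Section VII names no comparison for outcome 4. Its only covariate list (BMI, sex, age, new or established T1D) belongs to the logistic regression for rebound hyperglycemia. For CGM summaries by patient and day it plans mixed models of trajectories. It also plans to average each summary per patient and "compare the groups using t-tests or nonparametric equivalent". Rate of fall is not among the CGM summaries listed as examples, and no method is given for the glucometer version.

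**The concern.** A rate of fall is a change from a starting value. Under the protocol's own rules, a child who starts near 250 mg/dL soon receives dextrose to hold the level, while a child who starts much higher can fall freely for longer. Starting glucose is therefore likely to explain part of the variation between children in outcome 4. If the analysis leaves it out, that part stays in the error term.

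This matters more than usual because Hypothesis 3b predicts no difference and sets no margin. A wide interval that includes zero could be read as support for the hypothesis whatever the truth. The question is also one of safety: Sections III and IV.B give cerebral edema and hypoglycemia as reasons why adult data do not carry over to children. With about 24 children per arm, the arms can also differ by chance in starting glucose, and an unadjusted estimate carries that difference with it.

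**Working it through.** **The plan's own figure.** Section VII gives a total N of 48 for 30% versus 70% rebound hyperglycemia at 80% power. The two-sided 0.05 normal-approximation formula without continuity correction returns 24 per arm, or 48, with actual power 81.2%. All five columns of the power table reproduce (186, 122, 84, 48, 30). That figure is for the primary outcome; the plan states no power for outcome 4.

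**Inputs.** n = 24 per arm and alpha = 0.05 come from Section VII. Two-sided testing is assumed, since it is what reproduces the table. The correlation rho between presentation glucose and rate of fall is not in the documents, so 0.3, 0.5 and 0.7 are shown as assumptions. Effects are in SD units of the rate of fall.

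**Precision.** The standard error of an unadjusted difference is sqrt(2/24) = 0.289 SD. The noncentral t with 46 df gives 80% power at a difference of 0.826 SD. Adjustment multiplies the residual SD by sqrt(1 − rho²), and the equivalent sample-size factor is 1/(1 − rho²).

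| rho | sqrt(1 − rho²) | interval narrower by | power at 0.826 SD | sample-size factor |
|---|---|---|---|---|
| 0 (unadjusted) | 1 | 0% | 80% | 1 |
| 0.3 | 0.954 | 5% | 83.5% | 1.10 |
| 0.5 | 0.866 | 13% | 89.9% | 1.33 |
| 0.7 | 0.714 | 29% | 97.5% | 1.96 |

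Power here uses 45 df; a second covariate (44 df) changes it by less than 0.1 point. Multiplying the adjusted standard error by sqrt(1 + 1/44), to allow for estimating the glucose slope, gives 82.7%, 89.2% and 97.2%.

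**Chance imbalance.** The difference between arms in mean starting glucose has SD 0.289 SD. It exceeds 0.25 SD with probability 39%, 0.4 SD with probability 17% and 0.5 SD with probability 8%. Given an imbalance of k standard errors, the unadjusted test statistic has mean shifted by rho × k and variance 1 − rho². For k = 2 (2 × 0.289 = 0.58 SD):

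| rho | shift in estimate | conditional type I error | power for an 80%-power effect that the imbalance opposes |
|---|---|---|---|
| 0.3 | 0.17 SD | 8% | 60% |
| 0.5 | 0.29 SD | 13% | 43% |
| 0.7 | 0.40 SD | 22% | 22% |

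**Over all randomizations.** In 10,000 simulated trials with no true effect, the unadjusted t-test rejected in 5.4% (rho 0.5) and 5.0% (rho 0.7); ANCOVA rejected in 5.1% and 5.2%. The overall error rate is therefore sound either way. For a true difference of 0.6 SD, simulated power was 53% unadjusted and 65% adjusted at rho 0.5, and 52% and 80% at rho 0.7.

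**Does rho differ by window?** This is an illustration with invented inputs: uniform starting glucose, free fall of 75 ± 25 mg/dL per hour, and a level held once 150 to 250 mg/dL is reached.

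| assumed start (mg/dL) | rho, 0-2 h | rho, 2-4 h |
|---|---|---|
| 250-600 | 0.46 | 0.84 |
| 300-600 | 0.25 | 0.80 |
| 350-650 | 0.08 | 0.72 |

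The first-window figure depends heavily on the assumed range, because few children who start high reach the held level within 2 hours. The 2-4 hour figure stays high throughout.

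**The case against.** The strongest reply is that the plan never chose an unadjusted analysis. The t-test and mixed-model wording covers CGM summaries, and CGM is optional. A reader might infer from it that outcome 4 will be compared without adjustment, but Section VII does not say so; it says nothing on outcome 4. This stands. The defect is an unnamed analysis together with a set of methods none of which uses baseline glucose.

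A reader might also infer that leaving out starting glucose biases the comparison or produces false differences. It does not over repeated randomizations, where the error rate stays near 5%. The distortion exists only given the imbalance that one trial happens to draw.

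Third, rho is not in the documents. At 0.3 the gain is about 3 power points, and in the 0-2 hour window it could be close to nothing. This stands too, and no single power figure should be quoted for the outcome.

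Fourth, adjustment does not supply the missing margin in Hypothesis 3b. That is correct: it narrows the interval but does not settle what difference would matter.

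Finally, the choice of covariate needs care. Exclusion criterion 4 allows up to 6 hours of IV insulin before approach, so the last glucose before randomization may fall during or after an early window and would then not be a starting value. Presentation glucose avoids this.

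None of these replies removes the case for using a prognostic value that is already recorded.

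**Conclusion.** The point holds as a recommendation on one secondary safety outcome. Section VII should name an analysis for outcome 4, and that analysis should use presentation glucose. The link between starting level and fall rests on the protocol's own entry and dextrose rules; its strength is assumed. At 24 per arm, adjustment raises 80% power to about 83%, 90% and 97% for rho of 0.3, 0.5 and 0.7, with the later windows more likely to benefit than the first. The documents do not support a claim that the planned test is invalid, or that the primary analysis or N = 48 is affected.

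**What to change.** Add to Section VII:

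- **Model.** Outcome 4 is compared by ANCOVA in each window, or by one repeated-measures model over the four windows, with arm, T1D stratum and presentation glucose as terms. Say whether this applies to the glucometer version, the CGM version or both.
- **Covariate.** Use presentation glucose, which always precedes randomization. Do not adjust for glucose at the start of later windows: it may be post-randomization, and adjusting for it could remove part of the treatment effect.
- **Time 0.** Define the start of the windows. IV insulin may precede approach by up to 6 hours, early glargine waits for a pH threshold, and CGM may start up to 12 hours into treatment. Early windows may therefore precede randomization, glargine or the first CGM reading.
- **Reporting.** Give the adjusted difference between arms in mg/dL per hour with a 95% CI, so that Hypothesis 3b is judged on the interval and not on a non-significant p-value.

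The cost is a few sentences and one or two degrees of freedom out of 46. No new data are needed.

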- b. Assess the rate of blood glucose decrease while receiving IV insulin in children with DKA given early glargine versus standard-of-care management.
- c. Assess the number of participants who needed a decrease in their IV insulin rate between the two groups.

Hypothesis 4 (Exploratory): Continuous glucose monitoring (CGM) will be a feasible and useful tool during DKA treatment in children.

- a. CGM will agree with point-of-care (POC) blood glucose levels during DKA treatment in children.

Specific Aim 4 (Exploratory):

- a. To evaluate the agreement of CGM and POC glucose monitoring during DKA treatment in children.
- b. To determine the percent of CGM failures during DKA treatment in children.
- c. To describe the clinical importance of differences between CGM and POC glucose using Clarke error grid analysis.

In summary, this will be a clinical trial with aims to: 1) determine the rate of rebound hyperglycemia in children with DKA given glargine early in the treatment of DKA compared to those given glargine upon complete resolution of the metabolic acidosis (standard-of-care management); 2) evaluate the rate of recurrent ketogenesis in participants given early glargine compared to those given standard-of-care DKA management; 3) assess the risk of hypoglycemia between the two groups; and 4) evaluate the feasibility and utility of CGM as a tool to monitor blood glucose levels during DKA treatment in children.

The importance of this proposal relates to the research and clinical need to establish a smoother transition off of IV insulin in the management of DKA in children and to assess the utility of continuous glucose monitoring during treatment of DKA in children.

II. Background and Significance: *Explain the background of this project so that we will understand why it is important to perform this research project. (Approx. 1 page)*

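### The listed CGM outcome is a correlation, which cannot answer Aim 4a's question about agreement and has no matching analysis in the Data Analysis Plan; the effect is confined to an exploratory aim

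*Combined protocol and SAP*

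**What the plan says.** Section I frames the question as agreement. Hypothesis 4a reads "CGM will agree with point-of-care (POC) blood glucose levels during DKA treatment in children" and Specific Aim 4a reads "To evaluate the agreement of CGM and POC glucose monitoring during DKA treatment in children". Aim 4c adds "To describe the clinical importance of differences between CGM and POC glucose using Clarke error grid analysis". Aim 4 as a whole is labelled exploratory.

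Section IV.A, secondary outcome 6 (feasibility of CGM), has two bullets: the percentage of CGM failures, and "Correlation of CGM to POC glucose monitoring during DKA". No other listed outcome compares the two devices.

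Section VII (Data Analysis Plan) states that "Bland-Altman plots will be used to evaluate the agreement between CGM glucose variables (e.g., mean glucose) and POC glucose". For clinical relevance it adds that "we will use Clarke error grid analysis, which classifies pairs of blood glucose measurements made by two methods into categories". It mentions no correlation analysis. Neither section gives a correlation threshold, an acceptable bias or an acceptable width for the limits of agreement.

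**The concern.** The aim, the outcome and the analysis for one question do not line up. The aim and the analysis concern agreement; the outcome is a correlation. The listed outcome therefore has no planned analysis, and the planned agreement analyses have no listed outcome.

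The choice of word matters because correlation measures how closely two series follow a straight line, whatever that line is. A sensor that always reads a fixed fraction or a fixed amount too low keeps exactly the same r. Section VI says that CGM accuracy in dehydration is not well studied, so systematic error is an open question here, and it is the kind of error that r cannot show.

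There is a second, smaller issue. Section VII first reduces the CGM data to summaries per patient and day, then offers mean glucose as the example variable for Bland-Altman. Limits of agreement for averages describe the error of averages. A clinician reading one sensor value during DKA treatment needs the error of single readings.

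**Working it through.** **No plan figure to reproduce.** Aim 4 has no sample size, threshold or margin. The check is of what correlation and averaging do to the answer.

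**Inputs from the protocol.** Section C.2.1 says the sensor "has shown an average mean absolute relative difference (MARD) of 11.4% over 14 days of continuous wear". The same section gives the treatment range: "dextrose (5-12.5%) is added to the IV fluids to maintain serum glucose between 100 mg/dL and 200 mg/dL". Blood glucose is measured hourly on IV insulin.

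**Assumed inputs.** Normal proportional error; a constant bias factor b of 1 (none) or 0.75 (25% low); three glucose distributions: uniform 100-200, uniform 100-500, and mean 250 with SD 100 mg/dL; 12 hourly pairs per child.

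**Model.** CGM = b × POC × (1 + e), with e normal, mean 0, SD s. For b = 1, MARD = s × √(2/π) = 0.798 s, so s = 0.114/0.798 = 0.143 and s² = 0.0204.

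**Correlation.** Write m and v for the mean and variance of POC glucose, and K = s²(m² + v).

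- Cov(POC, CGM) = b·v
- Var(CGM) = b²(v + K)
- r = b·v / √(v · b²(v + K)) = √(v/(v + K))

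The factor b cancels. Adding a constant to every CGM value also leaves r unchanged.

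**Agreement.** Mean difference = (b - 1)m. Variance of the difference = (b - 1)²v + b²K. The 95% limits are the mean difference ± 1.96 SD.

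| POC glucose (mg/dL) | m | v | K | r, any b | b = 1: mean diff. (limits) | b = 0.75: mean diff. (limits) |
|---|---|---|---|---|---|---|
| Uniform 100-200 | 150 | 833 | 476 | 0.80 | 0 (-43 to +43) | -37.5 (-73 to -2) |
| Uniform 100-500 | 300 | 13,333 | 2,109 | 0.93 | 0 (-90 to +90) | -75 (-163 to +13) |
| Mean 250, SD 100 | 250 | 10,000 | 1,480 | 0.93 | 0 (-75 to +75) | -62.5 (-137 to +12) |

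Example, last row: r = √(10,000/11,480) = 0.933. With b = 0.75 the variance of the difference is 0.0625 × 10,000 + 0.5625 × 1,480 = 1,457.5, so SD = 38.2 and the limits are -62.5 ± 74.8. MARD goes from 11.4% to about 25%. The agreement measures register the bias and r does not. The level of r depends on the glucose range: 0.80 over 100-200 mg/dL and 0.93 over the wider ranges.

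**Averaging.** Take mean 250, SD 100 and no bias.

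- Single pairs: 1.96 × √1,480 = ±75 mg/dL.
- Mean of 12 pairs, independent errors: 75.4/√12 = ±22 mg/dL.
- Mean of 12 pairs, with e correlated 0.6 within a child and POC values independent: 1.96 × s × √(72,500/12 + (11/12) × 0.6 × 62,500) = 1.96 × 0.143 × 201 = ±56 mg/dL.

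A constant bias would still show in the mean difference of averages. What is understated is the scatter of single readings.

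**The case against.** The strongest reply is that the plan already has the right methods. Section VII assigns agreement to Bland-Altman by name, applies Clarke error grid analysis to pairs of measurements, and plans no correlation; Aim 4c makes the Clarke analysis an aim in its own right. On this reading the bullet in outcome 6 is a loose label for what Section VII does. In addition, Aim 4 is exploratory, CGM is optional and depends on funding, the sensor is blinded from the participant with data downloaded after about a week, and the primary outcome uses the glucometer. Most of this stands, and it sets the severity.

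A reader might infer more: that a badly biased sensor could be reported as valid in DKA. The documents do not support that. A sensor reading 25% low would appear as a negative mean difference on the planned Bland-Altman plot. Nor do the outcome list and the analysis plan yield competing answers, since no correlation result is planned and no threshold is set for one.

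It would also be too strong to say that r is bound to be high; it is about 0.80 over 100-200 mg/dL even without bias. The exact invariance holds only for a constant scale or shift. A bias that changes as a child rehydrates would in general move r, although r would still not give its size or direction. Only the 11.4% MARD and the 100-200 mg/dL range are the protocol's; the other inputs are illustrative.

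What the reply leaves standing is that the listed outcome is not the quantity the aim asks for, and that the Bland-Altman sentence does not specify time-matched readings or allow for repeated pairs from the same child.

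**Conclusion.** The point holds as a minor inconsistency. Secondary outcome 6 names a measure that cannot answer Aim 4a and that Section VII does not analyse. That correlation is blind to a constant bias is algebra and needs no assumption about glucose values; the figures for bias and limits rest on the assumed distributions and the assumed 25% bias. The Bland-Altman example, taken literally, would report limits of about ±22 to ±56 mg/dL where single readings have about ±75, assuming 12 pairs per child and within-child error correlation between 0 and 0.6. No sample size, randomised comparison or primary conclusion is affected.

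**What to change.** In Section IV.A, replace the second bullet of secondary outcome 6 with: agreement of time-matched CGM and POC glucose readings during DKA treatment, summarised by mean difference, 95% limits of agreement allowing for repeated pairs per child, MARD, and the percentage of pairs in each Clarke zone.

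In Section VII, change the Bland-Altman sentence so that it refers to time-matched pairs, state the matching window, and name the method that allows for repeated pairs within a child. If correlation is reported, present it as description and not as evidence for Hypothesis 4a.

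The cost is the wording of one outcome and one analysis sentence, and a little more analysis of data already collected. The agreement figures may look less favourable than a correlation would.
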